## 8.4.3.6. The Cause of Death Register

The Cause of Death Register is a national register containing information on date and cause of death (underlying and contributory) for all deceased residents, including deaths among Swedish residents who died abroad. Although the register was started in 1952, the data are considered complete since 1961 (de Faire et al., 1976).

#### 8.4.3.7. The Total Population Register

The Total Population Register lists data on residency at a given point in time since it was founded in 1961, and dates of emigration/immigration for all subjects ever resident in Sweden since 1961. This register thus provides information on censoring (death and emigration) of patients (Ludvigsson et al., 2016).

## 8.5. Study Size

This is a descriptive study without prespecified hypotheses. The goal is to obtain data on up to 500 eligible patients with UC initiating filgotinib during the observational period (per registry) and thus the study size will be dictated by the number of filgotinib patients identified in the participating registries. For illustrative purposes, by applying the rule-of-3 (Hanley & Lippman-Hand, 1983) and assuming an underlying proportion e.g. of a contraindication of 1%, implies that the contraindication would be detected with a certainty of 95% for a sample size of 300 patients; if the underlying proportion of contraindication is 2%, then a sample of 150 patients would suffice (see Table 3).

Underlying Proportion of Contraindication	Sample Size to Detect Contraindication
1%	300
2%	150
3%	100
4%	75
5%	60

 Table 3
 Sample Size Requirements to Detect Contraindication with 95% Certainty

In terms of precision, if the observed proportion of patients at high risk, for example MACE, is 10% among a sample size of 300 users of filgotinib, then this will be estimated with a precision (standard error) of 1.7% resulting in a 95% CI of 6.6% to 13.4% (Altman, 1999). Other scenarios of precision are provided in Table 4 and Figure 2.

Table 4	Standard Error	by Study S	Size and Under	lving Proportion
				J 8

	Study Size				
Proportion*	200	300	400	500	
2%	1.0%	0.8%	0.7%	0.6%	
5%	1.5%	1.3%	1.1%	1.0%	
10%	2.1%	1.7%	1.5%	1.3%	
15%	2.5%	2.1%	1.8%	1.6%	

\* Proportion of patients at high risk of MACE, VTE, or serious and opportunistic infection. Calculations are based on a normal distribution assumption for the proportion

# Figure 2 Estimated 95% Confidence Interval by Study Size and Underlying Proportion (Assuming a Binomial Distribution)

## 8.6. Data Management

## 8.6.1. ENEIDA (ES)

This study will involve analysis of secondary data from the ENEIDA registry, as described in Section 8.4. The automated data are maintained and managed by the ENEIDA registry in a password-protected MySQL database, which is maintained on a server in a secure facility. The investigator or qualified designee is responsible for verifying the accuracy of patient data as it is entered into the ENEIDA registry. All analyses will be conducted using SAS software.

This study involves chart review for all patients exposed to filgotinib identified in the automated data. Linkage between the automated record and the patient record will be based on the patient identification number and clinical site identifier.

Data will be accessed by Research Triangle Institute Health Solutions (RTI-HS) according to ENEIDA's standard practice. RTI-HS will log on to the ENEIDA secure server, download the data files, and store the data in a secure server in Barcelona with backups in the EU. Only selected RTI-HS personnel in Barcelona will have access to the data. Once the data are received,

RTI-HS will develop a data dictionary using SAS PROC CONTENTS. The data dictionary will document any data transformations applied to the received data sets to create the analytical datasets. The data dictionary will include variable names, formats, and any SAS code used to create derived variables from raw variables.

The transfers of data from ENEIDA may include data for patients who do not qualify for the analytic purposes of the present study. However, these data may be used to determine whether the analytic database is representative of the ENEIDA registry data in its totality. All data received from the registry will be covered by the IC signed by all patients at enrolment in ENEIDA. Chart abstraction will require patients to sign a study-specific IC to be able to obtain information of variables that are not part of the ENEIDA registry scope (see also Section 9.3.1). Data not used for the analysis will be filtered out at RTI-HS. Only data essential to the planned analyses will be retained in the analytic database.

## 8.6.2. ICC (NL)

The data management program of choice will be designed, built, provided, and supported by MEMIC, an information and communication technology-company affiliated to Maastricht University, Maastricht, the Netherlands. The database is designed for adequate and safe data recording, and MEMIC ensures that the strict rules concerning anonymity of medical data, access to the data and storage of the medical data are followed. The database is linked to a logistic program (called Logis) which will determine the moments of follow-up. Physicians will get an alert from the program when a new follow-up moment has to be scheduled for a patient.

The follow-up protocol is based on current standard of care (see Section 8.4.2). Visits are at initiation of therapy, at Week 12, 24, 52, 104, and once yearly thereafter. If patients stop therapy, a discontinuation visit form is filled in. A reminder for every visit is sent by email to the treating physician or nurse 3 weeks before the scheduled visit date.

Each participant is assigned a unique code, consisting of a number for each center and a 5-digit sequence number. This code will be used for all study-related documents and materials. The participant's identity cannot be traced directly via this code. Only the local principal investigator and local coordinating researcher will have access to the local source file, in which the unique code is linked to the personal data such as name and date of birth. This file will be kept in a secure site on the hospital/institutions network and access to this file will be restricted to the clinicians participating in the study at this local center.

All analyses will be conducted using the IBM SPSS Statistics for Windows, version 24.0 or higher (IBM, Armonk, NY).

## 8.6.3. SWIBREG (SWE)

This study analyses secondary data available through SWIBREG and several other nationwide registers. Researchers from the Karolinska Institute (KI) are responsible for the data management of this study. As previously described (Section 8.4.3), health and demographic information within Sweden is collected in a series of registers with a high degree of completeness resulting from the mandatory and semiautomated registration of their data. Based on each Swedish resident's unique

personal identification number, issued to all Swedish residents alive in 1947 or born/immigrated thereafter, linkage of data from different registers is possible. The registers are maintained by governmental bodies (the main registers used in this study are held by the National Board of Health and Welfare [Socialstyrelsen] and Statistics Sweden [Statiskiska centralbyrån]), who may perform data linkages and provide pseudonymized data for research purposes. The data obtained for this study will reside on restricted, double backed-up servers at the Clinical Epidemiology Division at the Karolinska University Hospital Campus. Trained statistician/epidemiologist staff will perform data linkage, in addition to data cleaning and analysis. All work with these data warehouses is done by trained staff in adherence with local guidelines on good programming, data management practices, and archiving. According to the Swedish law, the data, programs, and documents related to study reports will be maintained for a minimum of 10 years.

The data retrieval and linkage include the following steps:

- 1. At end of study follow-up (or data cut-off point for interim reports), data will be ordered from SWIBREG and the Swedish Board of Health and Welfare.
- 2. The data provider of SWIBREG (Health Solutions) will export quality register data to the Board of Health and Welfare.
- 3. The Board of Health and Welfare will create a study cohort, consisting of all included patients and send the list of their personal identification numbers to Statistics Sweden.
- 4. A list of all study participants will be sent back to the Board of Health and Welfare and there the study population will be linked to all the health registers.
- 5. A pseudonymized dataset consisting of all patients with UC will be sent to the study researchers at KI. The key to the dataset will be kept at the Board of Health and Welfare, which makes updates to the dataset possible in the future but identification of individual patients impossible for the researchers.

At KI standard statistical software including SAS, STATA, and R is used.

## 8.7. Data Analysis

Detailed methodology for the analyses of data included in this study will be documented in a common and harmonized statistical analysis plan (SAP), which will be created by the study coordinating center with input from investigators from the 3 registries, dated, filed, and archived by the MAH. Data analysis summarized in the protocol may be modified in the SAP to reflect usage of the most up-to-date methodology used by the different registries.

Data will be summarized using univariable descriptive statistical methods. Categorical outcome variables will be summarized by number and percentage of patients in each categorical definition including 95% CIs. Counts for missing values will be also tabulated but missing values will not be considered in the percentages. Continuous variables will be summarized descriptively (mean, standard deviation, and median, lower quartile, upper quartile, minimum, maximum).

#### Follow-up

Among women starting filgotinib, the number and proportion who become pregnant during follow-up will be reported. Similarly, the number and proportion of patients who have a new

diagnosis of TB during follow-up, a serious acute infection, a diagnosis of viral hepatitis, concomitant treatment with other immunosuppressants, or who are administered a live attenuated vaccine will be reported. In patients with TB, or a serious infection identified during follow-up, it will be assessed whether treatment was stopped or interrupted after the diagnosis. The proportion of patients who have a test for lipids at around 12 weeks since initiation of filgotinib will be reported.

Should a VTE event occur, subsequent changes to filgotinib use will be reported (filgotinib treatment persistence or discontinuation).

Assessment of the filgotinib maintenance dose during follow-up will also be done in the subgroup of patients at high risk of MACE, VTE, or malignancy. In addition, the average daily dose during the maintenance period and the duration of use during the follow-up period will be reported.

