The safety information in the HCP Guide provides context and risk management advice for key safety aspects of the SmPC, namely (key safety aspects with updates in the HCP Guide after Article 20 are listed in *italics*):

- Serious and opportunistic infections
- Herpes zoster
- Potential risk of birth defects if filgotinib is taken during pregnancy

- Potential risk of VTE
- Potential risk of MACE
- Potential risk of malignancy
- Prescribing in elderly patients and in patients with risk factors for VTE, MACE, and malignancy

The SmPC specifies that the recommended dose for induction treatment in UC is 200 mg once daily. The recommended dose for maintenance treatment is 200 mg once daily. In patients aged 65 years or older or at higher risk of VTE, MACE and malignancy, the recommended dose is 200 mg once daily for the induction treatment which may be prolonged up to Week 22, and 100 mg once daily for maintenance treatment. In case of flare of the disease, the dose may be escalated to 200 mg once daily. For long term treatment, the lowest effective dose should be used (as per SmPC Section 4.2 'Posology and method of administration').

In patients with active tuberculosis (TB), active serious infections, or in women who are pregnant treatment with filgotinib is contraindicated (as per SmPC Section 4.3 'Contraindications').

Additional aspects as per updated SmPC Section 4.4 'Special warnings and precautions for use' are listed below:

*Use in patients 65 years of age and older*: Considering the increased risk of MACE, malignancies, serious infections, and all-cause mortality in patients 65 years of age and older, filgotinib should only be used in these patients if no suitable treatment alternatives are available.

*Infections*: As there is a higher incidence of infections in the elderly and in the diabetic populations in general, caution should be used when treating the elderly and patients with diabetes.

*Malignancy*: In patients 65 years of age and older, patients who are current or past long-time smokers, or with other malignancy risk factors (e.g. current malignancy or history of malignancy), filgotinib should only be used if no suitable treatment alternatives are available.

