# 7. RESEARCH QUESTION AND OBJECTIVES

Information on prescribing of filgotinib for UC under real-world clinical practice is scarce, specifically, in the context of the updated prescribing information and HCP Guide after implementation of Article 20 decisions on JAKi's.

Therefore, this longitudinal DUS aims to describe physicians' adherence to the prescribing information of filgotinib in real-world clinical practice and to evaluate the effectiveness of the aRMMs by assessing how HCPs prescribing filgotinib adhere to the information provided in the SmPC in conjunction with the information in the HCP Guide with a specific focus on aRMMs implemented after the EC Article 20 decision on JAKi's (i.e. after 10 March 2023).

The objectives of this study are as follows:

- a. To describe the characteristics of patients treated with filgotinib in terms of:
- Demographics (e.g., age and sex)
- Comorbidities and prior and current medication use
- b. To evaluate prescribers' adherence to the filgotinib aRMMs, specifically:
- Compliance with the recommended posology (average daily dose) and duration of use
- Compliance with recommendations for patient screening and laboratory monitoring prior to and during treatment
- Compliance to recommendations for use in patients with moderate to severe chronic renal impairment/end stage renal disease or severe hepatic impairment
- Compliance with recommendations for limitations of use, including:
  - Use in patients with risk factors for venous thromboembolism (VTE)
  - Use in patients aged 65 years and older
  - Use in patients with risk factors for cardiovascular (CV) disease
  - Use in patients with risk factors for malignancy

- Use in patients with risk factors for serious infections
- Use in patients with concomitant use of other potent immunosuppressants
- Use of live attenuated vaccines
- Contraindicated use
- Compliance with discontinuation of filgotinib treatment in patients experiencing VTE

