#### 8.2.2. Inclusion Criteria

Across all 3 registries, adult patients ( $\geq$ 18 years) of any sex with UC that are enrolled in 1 of the 3 IBD registries after 10 March 2023 and during the observational period (complying with the register's requirements for inclusion including patient consent) and initiated on filgotinib after 10 March 2023. Initiation is defined as either no prior filgotinib use or prior use that was discontinued before 10 March 2023 (thus, patients who are non-naïve to filgotinib can be included).

There are no restrictions on patient inclusion in terms of either historical data or minimum amount of follow-up.

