## 8.2.4. Index Date, Follow-up

The index date (= start of follow-up) in each registry will be the date a patient starts UC treatment with filgotinib (i.e. the date of first identification of filgotinib exposure in the registry) after the EC decision date. The patient's total follow-up time is defined as the time from the filgotinib index date until the earliest of treatment discontinuation, study withdrawal (withdrawn from the registry, death or loss to follow-up) or end of study.

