Variable	Availability in individual registries yes/no (additional comments)		
	ENEIDA (ES)	ICC (NL)	SWIBREG (SE)
			hospitalizations with IBD as the main diagnostic listing will be treated as flares)
Date of hospitalization	no (might be in medical report)	yes	yes (NPR)
Hx of blood clotting disorder or blood clots	no (might be in medical report)	yes (as part of medical history/comorbidity)	yes (NPR)
Concomitant use of combined hormonal contraceptives	no (might be in medical report)	no (but can be added)	yes (NPR)
Concomitant use of hormone replacement therapy	no (might be in medical report)	no (but can be added)	yes (NPR)
SmPC section 4.6: Fertility, pregnancy and lactation			
Advice on contraception in women of childbearing potential	no	no	no
Breastfeeding	no (might be in medical report)	no (but can be added)	no
	Variables assessed during follo	w-up	
Filgotininb treatment status			
Discontinuation	yes	yes	yes (SWIBREG, PDR)
Date of discontinuation	yes	yes	yes (SWIBREG, PDR)
SmPC section 4.2: Posology (Maintenance treatment)			
Maintenance filgotinib dose (after a maximum of 22 weeks of induction treatment)	yes (if not available, might be in medical report)	yes	yes (PDR)
SmPC section 4.3: Contraindications			

Variable	Availabil (ad		ries
	ENEIDA (ES)	ICC (NL)	SWIBREG (SE)
Tuberculosis (TB)	yes (if not available, might be in medical report)	yes	yes (SmiNet)
Dx date TB	yes (if not available, might be in medical report)	yes	yes (SmiNet)
Serious infection (SI)	yes (if not available, might be in medical report; a proxy definition of infection severity can be used to align with the definition of the other registries, based on information available from an eCRF field on the outcome of the infection [such as death, hospital admission])	yes (infections that lead to hospitalization or intravenously administrated antibiotic or antiviral medication)	yes (ICD-10 codes as recorded in the NPR or the 'infectious disease register' [for tuberculosis] including overall codes for e.g. sepsis or septic shock or for specific infectious disease categories being the main or contributory diagnostic listing for a hospitalization)
Dx date SI	yes (if not available, might be in medical report)	yes	yes (NPR)
Pregnancy	yes (if not available, might be in medical report)	yes	yes (Medical Birth Register; could be retrieved following child birth)
Date of pregnancy	yes	yes	yes (Medical Birth Register; could be retrieved following child birth)

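### The follow-up pregnancy proportion uses all women starting filgotinib as its denominator, so women past childbearing age pull it below the proportion among women at risk

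*Protocol*

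**What the plan says.** The Follow-up part of Section 8.7 fixes the measure: "Among women starting filgotinib, the number and proportion who become pregnant during follow-up will be reported". It adds no restriction by age or childbearing potential, and no other section does.

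The eligible population is broad. Section 8.2.2 takes patients aged 18 years or more, "of any sex with UC that are enrolled in 1 of the 3 IBD registries after 10 March 2023", and sets no upper age limit. Section 7 lists "Use in patients aged 65 years and older" among the limitations of use to be assessed, so older patients are expected in the cohort.

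The measure relates to a contraindication. Section 6 reports the product information as follows: "In patients with active tuberculosis (TB), active serious infections, or in women who are pregnant treatment with filgotinib is contraindicated". Section 7 includes "Contraindicated use" in the adherence objectives, and Table 5 places pregnancy during follow-up in its contraindications block.

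Follow-up is on treatment. Section 8.2.4 says: "The patient's total follow-up time is defined as the time from the filgotinib index date until the earliest of treatment discontinuation", with registry withdrawal, death, loss to follow-up and end of study as the other end points.

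Table 5 marks date or year of birth, and sex, as available in all three registries.

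**The concern.** A proportion that describes exposure to a contraindication is most useful when its denominator holds the people in whom the event can occur. The protocol goes part of the way by leaving men out of this measure. It keeps women past childbearing age, who add to the denominator and can never add to the numerator.

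Three things follow. The proportion is lower than the one among women at risk. Its confidence interval looks tighter than the informative sample supports. And because each registry analyses its own data, two registries with the same pregnancy risk among younger women would report different proportions if their age mixes differ. Section 8.9 already warns that uneven data quality may inflate or mask real differences between registries. A denominator that varies with age mix adds another source of difference, and this one is avoidable.

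**Working it through.** **The plan's own figures.** The protocol gives no expected value for the pregnancy proportion. Its only figures on contraindications are in Table 3 (Section 8.5), from the rule of three, n = 3/p. For p = 1%, 2%, 3%, 4% and 5% this gives 300, 150, 100, 75 and 60, matching the table. The point below does not depend on them.

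**Inputs.**
- Denominator: all women starting filgotinib (Section 8.7, Follow-up).
- Age range: 18 years and over, no upper limit (Section 8.2.2).
- Sample size: up to 500 patients per registry (Section 8.5).
- Share of women among starters: not given. Assumed 50%, so 250 women. Section 6 says only that UC has no specific sex predominance.
- Share f of women starters who are of childbearing age: not given. Assumed range 0.5 to 0.8, so 50% to 20% are outside it.

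**Formula.** Let p be the proportion becoming pregnant among women of childbearing age. Pregnancies arise only in that group, so

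reported proportion = p × f, and p = reported / f.

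**From a reported 2.0% to the proportion among women at risk.**

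| Share outside childbearing age (assumed) | f | p = 2.0% / f |
|---|---|---|
| 20% | 0.8 | 2.5% |
| 30% | 0.7 | 2.9% |
| 40% | 0.6 | 3.3% |
| 50% | 0.5 | 4.0% |

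**In the other direction.** If p = 2%, the planned measure shows 2% × 0.8 = 1.6% down to 2% × 0.5 = 1.0%. If p = 5%, it shows 4.0% down to 2.5%.

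**Registry comparison.** Take p = 5% in two registries, one with f = 0.8 and the other with f = 0.5. They would report 4.0% and 2.5% with no difference among women at risk.

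**Precision.** With no pregnancies among 250 women, the rule-of-three upper bound is 3/250 = 1.2%. If 40% are outside childbearing age, 250 × 0.6 = 150 women remain and the bound is 3/150 = 2.0%.

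With 5 pregnancies among 250 women the proportion is 2.0%, exact 95% CI 0.7% to 4.6%. If 30% are outside childbearing age, 250 × 0.7 = 175 women remain, and the same 5 pregnancies give 2.9%, exact 95% CI 0.9% to 6.5%.

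**What does not change.** The number of pregnancies is the same under either denominator, and the protocol reports it.

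**The case against.** The strongest reply is that nothing is miscalculated. The proportion is correctly labelled as one among women starters, the study is descriptive with no hypotheses, no formal comparison of countries is planned, and the count is given beside it. All of that is right, and it is why the point is minor. It does not make the proportion informative about women at risk.

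Second, the size is assumed. The protocol gives no age or sex mix for filgotinib starters, and Section 6 says UC most commonly affects adults aged 30 to 40, so the diluting share could lie at or below the low end of the range. The shift is also modest beside the sampling uncertainty, as the overlapping intervals above show. This stands. The direction, however, is fixed, and dilution persists whatever the sample size.

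Third, Section 8.7 lets the statistical analysis plan modify the analysis, and that plan could add an age-restricted line. It could. But the protocol states this denominator outright and does not leave it open, and a plan that follows the protocol will carry it forward.

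A reader might also infer more than the text supports:
- That pregnancy at the index date is diluted by a further factor of 2 because men are counted. Section 8.3.1 lists that variable without a denominator. The general rule in Section 8.7 about percentages of patients does not establish one, and where the protocol does state a pregnancy denominator it excludes men.
- That Table 5 itself prescribes the narrower group. The row "Advice on contraception in women of childbearing potential" concerns counselling and is marked unavailable in every registry. It is not tied to the pregnancy rows.
- That non-pregnant older women are formally classed as compliant. No section does this.
- That the denominators for hormonal contraceptives or hormone replacement therapy are wrong. The protocol does not state them.

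**Conclusion.** The point holds for the follow-up pregnancy proportion in Section 8.7, as a minor one. The stated denominator includes women in whom the event cannot occur, so the proportion is below that among women of childbearing age by a factor equal to their share of women starters. For an assumed 20% to 50% outside childbearing age, a reported 2.0% corresponds to 2.5% to 4.0%. The direction follows from Sections 8.2.2 and 8.7 as soon as any woman past childbearing age is enrolled, and the objective on use at 65 and over makes that expected. The size rests wholly on the assumed share. What is affected is the proportion, its confidence interval and any reading across registries. The count of pregnancies is sound.

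**What to change.** In Section 8.7 (Follow-up), report the number and proportion becoming pregnant during follow-up among women of childbearing age at the index date. Use one age band, defined in advance and common to all three registries. Keep the figure among all women starting filgotinib as a secondary line.

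The cost is one sentence. Date or year of birth and sex are already available in every registry, so no new data are needed. The denominator becomes smaller and the confidence interval wider, which better reflects the information available. An age band only approximates childbearing potential, which is not a listed variable, and the report should say so.

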## 8.3.2. Follow-up Variables

Follow-up variables assessed during filgotinib treatment will include (as per availability by each registry):

- Filgotinib maintenance dose and average daily dose
- Diagnosis of TB
  - Date of diagnosis
- Serious acute infection
  - Date of diagnosis
- Diagnosis of viral hepatitis
  - Date of diagnosis
- Diagnosis of herpes zoster
  - Date of diagnosis
- Pregnancy
  - Start of pregnancy
- Use of live-attenuated vaccines
- Laboratory monitoring of lipids (total cholesterol, high- and low-density lipoproteins [HDL, LDL], triglycerides) around 12 weeks after initiation of filgotinib treatment and thereafter
- Laboratory measurements (any time during follow-up)
  - ANC
  - ALC
  - Hb
- VTE event
  - Date of VTE diagnosis

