#### 8.4.2.4.2. Follow-up Visits (Week 12, 24, 52, Year 2, 3, 4, 5, 6, 7, 8, 9, 10)

During follow-up visits, the following information is collected: current clinical disease activity (HBI/SCCAI), biochemical data (Hb, thrombocytes, leucocytes, ALT, alkaline phosphatase, CRP, creatinine, fecal calprotectin), current IBD medication, complications (surgery, hospitalization), AEs (events related to medication and infections), and, if applicable, radiologic and endoscopic information.

Details of variables to be collected in ICC can be found in Annex 3 – Table 5.

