Immunomodulators /- suppressants (e.g. tacrolimus, azathioprine, mercaptopurine)	yes	yes	yes	
Other (aminosalicylates, corticosteroids)	yes (not always available; might be in medical report)	yes	yes	
Reasons for switching	yes	yes	yes (SWIBREG, good coverage for targeted therapies)	
Intolerance/adverse events	yes	yes	yes	
Lack of efficacy	yes	yes	yes	
Other	yes	yes	yes	
SmPC section 4.1: Indication				
Severity of UC (moderate to severe)	yes (some data in ENEIDA may be available or alternatively through chart abstraction [through proxies such as drug switching, addition of drugs, colectomy etc.])	yes (SCCAI, CRP, fecal calprotectin and if available radiologic and endoscopic information)	yes (Severity of UC based on proxies such as exposure to immunomodulators or different lines of targeted therapies (= moderate to severe UC) or proxies for flares (e.g., steroid prescriptions, steps in the treatment ladder, hospitalizations with UC as main diagnosis, UC-related surgery, extent/location of	

Variable	Availability in individual registries yes/no (additional comments)			
	ENEIDA (ES)	ICC (NL)	SWIBREG (SE)	
			disease in UC, history of prior biologic use, disease duration and UC-related treatment exposure)	
Date of severity assessment	yes (if defined by medical therapies)	yes	yes	
Date of filgotinib initiation (to ascertain new users) = index date	yes	yes	yes	
Age at index date	yes	yes	yes	
SmPC section 4.2: Posology (Induction treatment)				
Initial filgotinib dose (induction treatment)	yes (if not available, might be in medical report)	yes	yes	
SmPC section 4.3: Contraindications				
Active TB at index date	yes (if not available, might be in medical report)	yes	yes (SmiNet, Population Register)	
Dx date TB	yes (if not available, might be in medical report)	yes	yes (SmiNet, Population Register)	
Active serious infection (SI) at index date	yes (if not available, might be in medical report)	yes	yes (Population Register, PDR)	
Dx date SI	yes (if not available, might be in medical report)	yes	yes (Population Register, PDR)	
Current pregnancy at index date	yes (if not available, might be in medical report)	yes	yes (Medical Birth Register)	

Variable	Availability in individual registries yes/no (additional comments)				
	ENEIDA (ES)	ICC (NL)	SWIBREG (SE)		
Date of pregnancy	yes	yes	yes (Medical Birth Register)		
SmPC section 4.4: Special warnings and precautions for use (Box warning)					
(Age 65+)	yes	yes	yes		

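### The high-risk posology depends on flare, but flare is neither a listed follow-up variable nor linked to the maintenance-dose assessment

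*Protocol*

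**What the plan says.** Section 6 summarises the posology against which adherence is assessed. For patients aged 65 or older, or at higher risk of VTE, MACE or malignancy, it gives "100 mg once daily for maintenance treatment" after induction and then adds: "In case of flare of the disease, the dose may be escalated to 200 mg once daily". Section 7 lists as its first adherence objective "Compliance with the recommended posology (average daily dose) and duration of use".

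The measurement side reads as follows.

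- **Section 8.3.2.** The dose item is "Filgotinib maintenance dose and average daily dose". The other items cover infections, viral hepatitis, zoster, pregnancy, vaccines, laboratory tests and VTE.
- **Section 8.7, Follow-up.** "Assessment of the filgotinib maintenance dose during follow-up will also be done in the subgroup of patients at high risk of MACE"; thromboembolic and cancer risk are named alongside. The sentence that comes next deals with dose over time and states that "the average daily dose during the maintenance period and the duration of use during the follow-up period will be reported".
- **Annex 3, Table 5.** Severity of UC stands in the baseline block. The follow-up block covers discontinuation, maintenance dose, contraindications, infections, viral reactivation, lipids, haematology and VTE.

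Flare-related data do appear elsewhere. For ICC, Section 8.4.2.4.2 says: "During follow-up visits, the following information is collected: current clinical disease activity (HBI/SCCAI", together with CRP and fecal calprotectin. For SWIBREG, the baseline severity row of Table 5 names "proxies for flares (e.g., steroid prescriptions, steps in the treatment ladder, hospitalizations with UC as main diagnosis", and the recent-hospitalization row, which belongs to the VTE risk factors, treats admissions with IBD as main diagnosis as flares. None of these entries is tied to dose.

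**The concern.** Whether a recorded dose in a high-risk patient fits the quoted posology depends on whether the patient had a flare. The listed variables give the dose without that condition. A high-risk patient escalated in a flare and one on the same dose for the same time without a flare produce identical entries.

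Posology compliance is an adherence objective of a study meant to show whether the risk minimization measures work. A reader of the report will take the share of high-risk patients at the higher dose as information on prescribers. Part of that share will reflect how often the disease flared.

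The protocol meets a similar problem with the condition that no suitable alternative is available. There, Section 8.9 admits the limitation and offers treatment history and reasons for switching as partial mitigation. The flare condition gets no variable, no mitigation and no stated limitation.

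**Working it through.** The protocol states no figure on this point, so there is none to reproduce. The check is a comparison of passages, followed by an illustration.

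**1. What the rule needs and what is listed**

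| Needed to read a high-risk maintenance dose against Section 6 | Section 8.3.2 | Table 5, follow-up block | Section 8.7 |
|---|---|---|---|
| Dose | yes | yes | yes |
| Flare or disease activity, dated | no | no | no |
| Reason for dose change | no | no | no |

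**2. What each registry could supply**

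- **ICC:** HBI/SCCAI, CRP and calprotectin at Weeks 12, 24 and 52, then yearly (Sections 8.4.2.4 and 8.4.2.4.2). A flare between yearly visits may be missed.
- **SWIBREG:** flare proxies and IBD hospitalizations (Table 5). Dose timing is coarse, because one dispensing is assumed to last 180 days (Section 8.3.3.3).
- **ENEIDA:** only severity proxies in the baseline block, with chart abstraction as the alternative source. Section 8.7.1.1 takes absent information as absence of the condition in most instances, so an unrecorded flare could become no flare by default.

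**3. Size, under assumed values**

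Let q be the share of high-risk patients outside the posology and f the share of the rest escalated in a flare. The documents give neither. The share seen at the higher dose is q + (1 − q) × f.

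| q | f = 10% | f = 20% | f = 40% |
|---|---|---|---|
| 0% | 10% | 20% | 40% |
| 5% | 14.5% | 24% | 43% |
| 10% | 19% | 28% | 46% |

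For example, 0.05 + 0.95 × 0.20 = 0.24. Only q concerns adherence.

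**4. Average daily dose for one patient**

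With a share t of maintenance time on 200 mg and the rest on 100 mg, the average is 100 × (1 − t) + 200 × t. For t = 10%, 25% and 50% this gives 110, 125 and 150 mg/day. The result is the same whether or not that time followed a flare.

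**The case against.** Five arguments stand against a stronger reading.

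- **No passage calls an escalation a deviation.** The study is descriptive. Section 8.7 sets no threshold and defines no non-adherent share. A reader might infer that allowed escalations will be counted as non-adherence, but the text does not say so. What it supports is that the output cannot tell the two apart.
- **Flare data partly exist.** A reader might infer that separation is impossible in every registry. ICC visit data and the SWIBREG proxies contradict that. The missing parts are the listing and the link to dose.
- **A group mean of 150 mg/day is not decisive.** It might seem that the mean hides whether all patients spend half their time on each dose, or half the patients stay on each dose throughout. Section 8.7 also reports SD, quartiles and range. In the first case the SD is 0; in the second it is about 50 mg, with a range of 100 to 200. The planned summaries separate these cases. They do not separate the same dose pattern with and without a flare.
- **Registry ranking.** A reader might infer that registries with more active disease will be judged less adherent. No comparative test is planned, and Section 8.9 already warns that differences between registries may be inflated or masked.
- **Analysis detail belongs in the SAP.** This stands for look-back windows and derivation rules. It does not cover the variable itself. Section 8.3 refers to Table 5 for the variables of interest, and an item left off the ENEIDA abstraction form cannot be analysed later.

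**Conclusion.** The point holds in limited form. The posology quoted in Section 6 is conditional on flare for high-risk patients, while Section 8.3.2, Section 8.7 and the follow-up block of Table 5 carry no flare status. These passages must be reconciled. As specified, the posology result in this subgroup mixes escalation in a flare with use of the same dose without one.

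Partial separation is within reach for ICC and SWIBREG. The gap is firmest for ENEIDA, where no follow-up source for flare is described.

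The documents do not allow the size to be estimated. The 10% to 46% range above follows only from the assumed q and f and shows how far the share at the higher dose can exceed q; it is not a forecast. This is a worthwhile correction to the variable list and the reporting, and it does not threaten the study as a whole.

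**What to change.** 1. **Section 8.3.2 and Table 5, follow-up block:** add a dated flare or disease-activity item. Sources are the ICC visit data, the SWIBREG proxies and IBD hospitalizations, and one ENEIDA chart-abstraction item. Exclude any filgotinib dose change from the SWIBREG proxies: treatment-ladder steps are among them, and a flare would otherwise be inferred from the escalation it is meant to explain.
2. **Section 8.7:** report high-risk maintenance dose by level, split into flare documented, no flare documented and flare unknown. State that unknown never defaults to no flare, notwithstanding Section 8.7.1.1. Keep average daily dose as a descriptive summary. Do not use the no-flare share as the sole indicator, because missed flares would then count against prescribers.
3. **Section 8.9:** state the misclassification that remains.

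The cost is protocol wording, one derived variable per registry and one item on the ENEIDA form, which is best added before the form is fixed. The limits should be stated openly. Proxies are imperfect and ICC visits are sparse after Week 52. ENEIDA flare data will be absent from the interim report, which uses no chart abstraction, and for patients without study-specific consent. Some episodes will stay unclassified. The change concerns measurement only and takes no position on dose.
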